5.3 LIFESTYLE CONSIDERATIONS

While participating in this trial, participants are asked to:

- Refrain from alcohol consumption of more than 20 g/2 units/2 standard drinks per day.
- Refrain from tobacco use (includes smoking, e-cigarettes, vaping, and other nicotine use) throughout the study.
- Abstain from any alcohol for the duration of clinical trial unit confinement.
- Abstain from any illicit drug habituation.
- Refrain from eating food containing poppy seeds for 48 hours prior to screening, malaria inoculation, and IMP administration.
- Refrain from excessive consumption of beverages or food containing xanthine bases including Red Bull, chocolate, coffee etc. (more than 400 mg caffeine per day, equivalent to more than 4 cups of coffee per day).
- Refrain from consumption of quinine containing foods/beverages such as tonic water and lemon bitter.
- Abstain from strenuous exercise and/or altering their regular exercise program.

5.4 SCREEN FAILURES

A screen failure occurs when a volunteer consents to participate in the clinical study but is not subsequently enrolled (inoculated with the malaria challenge agent). Volunteers who do not fulfil all the inclusion criteria, and/or fulfil any of the exclusion criteria, should not be enrolled. However, repeat assessments may be performed to confirm and follow-up on out-of-range clinical laboratory test, vital sign, and/or ECG values that determine a volunteer's eligibility.

If a volunteer does not meet all eligibility criteria, and is hence a screen failure, but at some point in the future is expected to meet the eligibility criteria, the volunteer may be re-screened for future cohorts. Volunteers who are re-screened will be re-consented and assigned a new volunteer number and then restart a new screening phase.

A minimal set of screen failure information is required to ensure transparent reporting of screen failure participants, to meet the Consolidated Standards of Reporting Trials (CONSORT) publishing requirements and to respond to queries from regulatory authorities. Minimal information includes demography, and screen failure details with respect to the eligibility criteria. Screen failure information will not be entered into the eCRF. Volunteers who fail screening due to an underlying medical condition previously unknown to them will be reimbursed for their time, and provided with the appropriate referrals for guidance and counselling for their condition.

5.5 STRATEGIES FOR RECRUITMENT AND RETENTION

Up to 18 healthy, adult, malaria-naïve participants will be enrolled in this trial. It is anticipated that up to 9 reserve participants will be required on Day 0 (3 per cohort) to ensure an adequate number of participants are enrolled and administered the malaria challenge agent.

Participants will be recruited by general or trial specific advertising via print, radio, social media, poster or other media, as approved by the HREC(s).

Participants who withdraw or are withdrawn from the trial will be compensated on a fractional basis for their involvement unless they are withdrawn as a consequence of their misconduct.

Reserve participants who do not participate in the trial will be compensated for the inconvenience associated with their attendance for screening and attendance on Day 0.

The monetary value of the compensation is documented in the Participant Information Sheet.

6 STUDY INTERVENTION

6.1 STUDY INTERVENTIONS ADMINISTRATION

6.1.1 STUDY INTERVENTION DESCRIPTION

IMP

MMV367 belongs to the pyrrolidinamide class of antimalarial compounds discovered using a high-throughput whole cell phenotypic screen. Preclinical studies indicated that MMV367 exhibits potent antimalarial activity against blood-stage *P. falciparum*, with a novel mode of action involving acyl coenzyme A synthetase 10 and 11.

Challenge agent

A *P. falciparum* 3D7 master cell bank (MCB) was produced from a participant with type O Rh (D) negative blood who was infected with the parasite by mosquito bite. Blood was collected and aliquoted into cryovials and stored in liquid nitrogen under controlled conditions. A cryovial will be retrieved from storage, thawed, and used to aseptically prepare the intravenous inoculum at Q-Gen Cell Therapeutics (QIMR Berghofer).

Definitive antimalarial medications

Riamet® (Novartis Pharmaceuticals Australia Pty Ltd) is an oral fixed dose combination therapy containing artemether and lumefantrine. Riamet® is registered in Australia for the treatment of acute uncomplicated malaria.

Malarone® (GlaxoSmithKline Australia Pty Ltd) is an oral fixed dose combination therapy containing atovaquone and proguanil hydrochloride. Malarone® is registered in Australia for the treatment of acute uncomplicated malaria.

Primaquine (Boucher & Muir Pty Ltd) contains the active ingredient primaquine phosphate. Primaquine phosphate is an 8-aminoquinoline effective against the sexual forms (gametocytes) of *Plasmodium* species which are responsible for transmission to mosquitoes. Primaquine is registered for use in Australia.

Artesunate (powder and diluent for reconstitution, imported by Link Pharmaceuticals) is an artemisinin derivative; the intravenous formulation is typically used to treat severe malaria. Although parenteral artesunate does not currently have marketing approval in Australia, the Therapeutic Goods Administration (TGA) allows importation of artesunate for Category A use in patients with severe malaria under the Special Access Scheme (SAS).

6.1.2 DOSING AND ADMINISTRATION

IMP

A single oral dose of MMV367 will be administered on Day 8 after an overnight fast of ≥ 8 hours. The IMP will be administered as an oral suspension in sterile water. Specific dosing instructions will be documented in the pharmacy manual. Participants will be required to remain fasted for 4 hours after dosing. Different doses of MMV367 will be tested across and within cohorts.

The doses to be tested in Cohort 1 will be as follows:

MMV367 dose	20 mg	90 mg	1500 mg
Number of participants	3	2	1

Specific doses to be tested in subsequent cohorts will be decided by the SDRT based on emerging data during the study (safety, PK, and PD data from preceding cohorts). The maximum dose to be tested in the study will be no more than 1500 mg.

Challenge Agent

The malaria challenge agent, containing an estimated 2,800 viable *P. falciparum* 3D7 parasite-infected erythrocytes in a volume of 2 mL, will be administrated intravenously on Day 0. The actual number of parasites inoculated will take into account the loss of viability resulting from cryopreservation, storage and thawing. Participants will undergo intravenous cannulation. The inoculum will be injected, and the cannula flushed with clinical grade saline. The cannula will then be removed. An extra syringe will be prepared to quantify the parasite count of the challenge agent by PCR.

Definitive antimalarial medications

Compulsory definitive antimalarial treatment for all participants will be initiated on Day 24, if not initiated earlier in accordance with the criteria described in Section 4.1.

Riamet® tablets will be administered as six oral doses of four tablets (total course of 24 tablets equivalent to 480 mg artemether and 2.88 g lumefantrine). The second dose of four tablets will be administered 8±1 h after the first dose. The remaining doses will be administered twice daily (morning and evening).

Malarone® will be utilised as a backup medication to Riamet® in the event of allergy or contraindication to Riamet®. A treatment course consists of four tablets administered daily for three days (total course of 12 tablets equivalent to 3 g atovaquone and 1.2 g proguanil hydrochloride).

Participants may be treated with Primacin® at the Investigator's discretion to ensure clearance of gametocytes. If needed, participants will be administered a single oral dose of six Primacin® tablets (total dose 45 mg primaquine) with food.

Intravenous artesunate may be administered in the event a participant vomits or cannot tolerate oral drugs. In this case, the participant will be admitted to hospital for treatment. Artesunate will be administered as 2.4 mg/kg IV bolus on admission, with repeat dosing at 12 hours and 24 hours, then once daily until oral therapy is possible.

6.2 PREPARATION/HANDLING/STORAGE/ACCOUNTABILITY

6.2.1 ACQUISITION AND ACCOUNTABILITY

Acquisition

IMP

MMV367 was manufactured by Piramal Pharma Solutions (India). The Sponsor will provide the IMP to the clinical trial unit.

Challenge agent

Aliquots of the *P. falciparum* 3D7 MCB are stored in liquid nitrogen under controlled conditions at QIMR Berghofer. On the day of inoculation, cryovials will be retrieved from storage and used to aseptically prepare the challenge agent at Q-Gen Cell Therapeutics (QIMR Berghofer). The challenge will then be transported to the clinical trial unit under controlled conditions.

Definitive antimalarial medications

Riamet® (distributed by Novartis Pharmaceuticals Pty Ltd), Primacin® (distributed by Boucher & Muir Pty Limited), and Malarone® (distributed by GlaxoSmithKline Australia Pty Ltd) will be acquired by the clinical trial unit. Artesunate for intravenous administration is available within the Central Pharmacy of Queensland Health.

Accountability

The clinical trial unit pharmacist or delegate is responsible for maintaining accurate study intervention accountability records throughout the study. Dispensing, accountability and documentation will be in accordance with the clinical trial unit standard procedures.

All products will be inventoried upon receipt by the clinical trial unit pharmacist. The condition of the products at the time of receipt by the pharmacist will be documented, as will the time restrictions of use for the syringes containing the challenge agent. The clinical trial unit pharmacist or designee will be responsible for maintaining the accurate *Plasmodium falciparum* 3D7 Challenge Agent Accountability Log as per clinical trial unit standard operating procedures (SOPs). The lot numbers and expiry dates of all study interventions will be documented. The clinical trial unit pharmacist or delegate will ensure that the received products are the specified formulation.

The storage, handling and the disposal of the products will be in accordance with approved procedures. All dosages prescribed and dispensed to the participants and all dose changes during the study must be recorded in the eCRFs and accountability logs. All drug supplies are to be used only in accordance with this protocol, and not for any other purpose. All used medications will be fully documented. All used product containers and packaging (and unused IMP and challenge agent) must be destroyed at the clinical trial unit once drug accountability is final and has been checked by the Sponsor or its delegate, and written permission for destruction has been obtained from the Sponsor.

Study products and study accountability logs will be available to the Sponsor or their representative as part of the study monitoring procedures. Upon completion of the study, copies of all study drug management records will be provided to the Sponsor. Original records will be maintained at the clinical trial unit with the rest of the study records.

6.2.2 FORMULATION, APPEARANCE, PACKAGING, AND LABELLING

The contents of the dispensing labels for the IMP, the malaria challenge agent, and the definitive antimalarial medications will be in accordance with all applicable regulatory requirements.

IMP

MMV367 is formulated as dispersible granules (250 mg/g [25% w/w]). The drug substance was blended with excipients (mannitol, microcrystalline cellulose, povidone, sodium lauryl sulfate, xanthan gum and fumed silica) to improve its oral bioavailability. Aliquots of the powder will be reconstituted in sterile water for oral administration of different doses.

Challenge agent

The malaria challenge agent will contain parasitised and unparasitised erythrocytes, resuspended in 0.9% Sodium Chloride Intravenous Infusion, in a total volume of 2 mL in syringes. The syringes will be double contained following preparation and labelled in accordance with GCP guidelines. Labelling is in accordance with PIC/S Annex 13.

Definitive antimalarial medications

Riamet® tablets (each containing 20 mg artemether/120 mg lumefantrine) are yellow, round, flat tablets marked with N/C and a score line on one side and CG on the other side. Each carton contains 24 tablets.

Malarone® tablets are round, pink and film-coated, and are engraved with “GX CM3”. Malarone® tablets are supplied in blister packs of 12 or 24 tablets.

Primacin® tablets (each containing 13.2 mg primaquine phosphate equivalent to 7.5 mg primaquine) are round, flat, orange uncoated tablets available in bottles of 28 or 56 tablets.

Artesunate powder for reconstitution is supplied in vials containing 60 mg artesunate. Each vial is reconstituted with an ampoule (1 mL) of sodium bicarbonate 5%. Sodium chloride 0.9 % (5 mL) is then added to reconstituted artesunate vial to create a 10 mg/mL solution (total volume 10 mL).

6.2.3 PRODUCT STORAGE AND STABILITY

All study interventions will be held in appropriate locked storage conditions at the clinical trial unit until required.

IMP

MMV367 dispersible granules are to be stored between 15°C and 25°C and protected from moisture. The reconstituted IMP for oral administration should be prepared within 8 hours of each administration.

Challenge agent

The *P. falciparum* 3D7 challenge agent is prepared at Q-Gen on inoculation day (Day 0). The time between preparation of the challenge agent and administration to the participant will be a maximum of 4 hours. The syringes containing the challenge agent will be stored in a temperature monitored validated transport container at 2-15°C during transportation from Q-Gen to the clinical trial unit and will be immediately transferred to a temperature monitored onsite refrigerator (2-15°C). The clinical trial unit pharmacist or delegate will document receipt conditions and time restrictions of use. The challenge agent will then be dispensed to participants as per written prescription. Transporter logs should be provided to the Sponsor.

Definitive antimalarial medications

Riamet® tablets are to be stored below 30°C and protected from moisture. Primacin® tablets are to be stored below 25°C. Malarone® tablets are to be stored below 30°C. The reconstituted artesunate for intravenous administration should be prepared freshly for each administration and should not be stored.

6.2.4 PREPARATION

IMP

The IMP will be prepared at the clinical trial unit by reconstituting the dispersible granules in sterile water for oral administration. Detailed preparation instructions will be provided in the pharmacy manual.

Challenge agent

The challenge agent will be prepared aseptically at Q-Gen from frozen cryovials of the *P. falciparum* 3D7 MCB by nominated QIMR Berghofer staff members. The erythrocytes will be thawed, washed, resuspended in saline, diluted in a final volume of 2 mL of clinical grade saline, and dispensed into syringes. Any remaining unused erythrocytes will be discarded as per approved SOPs.

Definitive antimalarial medications

Riamet®, Primacin® and Malarone® are available as tablets and no preparation is required. Artesunate for intravenous administration will be prepared according to manufacturer's instructions within the hospital setting immediately prior to administration.

6.3 MEASURES TO MINIMIZE BIAS: RANDOMIZATION AND BLINDING

All participants will receive an identification number (screening number) as soon as they have signed the informed consent form. Participants who meet the eligibility criteria and are enrolled in the study will be assigned an enrolment number on Day 0 immediately prior to administration of the malaria challenge agent. Participants will be randomised within each cohort to a dose group on Day 8, immediately prior to administration of the IMP. A randomisation schedule will be prepared in advance and take in account potential participant withdrawals prior to scheduled dosing with IMP. The details of the randomisation procedure will be described in the randomisation plan. This is an open label study and therefore no blinding will be performed.

6.4 STUDY INTERVENTION COMPLIANCE

The Investigator will administer the malaria challenge agent intravenously at the clinical trial unit on Day 0. The IMP (single oral dose of MMV367) will be administered in a fasted state at the clinical trial unit on Day 8 under direct observation by staff. The first dose of definitive antimalarial medication (Riamet®, or Malarone® if required) will be administered at the clinical trial unit under direct observation by staff (except in the event a participant tests positive to COVID-19; See Section 8.2.6.11 for details of COVID-19 management plan). The subsequent doses may be taken at home. Participants will receive a phone call or text message from the clinical trial unit staff to ensure compliance.

If Primacin® is required to clear gametocytaemia, it will be administered at the clinical trial unit under direct observation by staff. If a participant requires intravenous artesunate, the participant will be admitted to hospital for treatment.

6.5 CONCOMITANT THERAPY

Concomitant medications, treatments and procedures are those occurring from the time of administration of the malaria challenge agent (Day 0), until EOS. Those occurring prior to Day 0 are

classified as prior medications, treatments and procedures. Medications taken within 28 days before Day 0 will be recorded as prior medication.

On Day 0, participants will be questioned in relation to relevant aspects of compliance with the study protocol, including drug intake since their screening visit. Details of all drugs taken (prescription and over-the-counter, systemic and topical administration) will be recorded at this time and appropriate action taken.

From Day 0 until the EOS visit, no medications will be permitted to be taken without the approval of the Investigator (with the exception of contraceptives and ibuprofen/paracetamol). Ibuprofen (preferred) may be administered at doses of up to 1.6 g/24 hours, or paracetamol up to 4 g/24 hours with investigator approval, for treatment of headache or other pain if required. Ibuprofen is the preferred treatment for headache or pain. To minimise the risk of liver enzyme elevation, use of paracetamol should be kept to a minimum if possible. However, since paracetamol may be required by some participants its use is not excluded. All other medications will be assessed by the investigator on a case by case basis with regard to the participant's wellbeing and potential for the medication to interfere with study interventions.

Any medication taken during the study for treatment of a medical condition or AE is to be recorded in the concomitant medication pages in the eCRF. The exact dose, route and timing of each dose should be recorded.

6.5.1 RESCUE MEDICINE

All participants will be administered definitive antimalarial treatment in this study. Details of these medications are included in Sections 6.1 and 6.2.

7 STUDY INTERVENTION DISCONTINUATION AND PARTICIPANT DISCONTINUATION/WITHDRAWAL

7.1 DISCONTINUATION OF STUDY INTERVENTION

Once inoculated with the challenge agent on Day 0, it is expected that some study participants may experience mild to moderate malaria signs and symptoms prior to scheduled dosing with the IMP on Day 8. The following criteria should be considered as guidance for the decision not to proceed with administration of the IMP on Day 8 and to administer definitive antimalarial treatment instead:

1. A participant experiences an SAE or severe AE (\geq CTCAE Grade 3).
2. A participant returns a positive alcohol or urine drug screen.
3. A participant tests positive for SARS-CoV-2.
4. Investigator decision based on other safety signals (clinical, ECG, vitals and laboratory tests) not included in the above criteria if there is a perceived risk to participants.

In the event that definitive antimalarial treatment is initiated instead of dosing with the IMP, participants will be administered their first dose of antimalarial medication at the clinic (except in the event a participant tests positive to COVID-19; See Section 8.2.6.11 for details of COVID-19 management plan) but will then be able to return home. The participant will be contacted daily via phone to check that each dose of antimalarial treatment is being taken, and to ascertain any AEs. Following antimalarial treatment, blood will be taken for malaria PCR until at least one negative result is obtained. The participant will then be withdrawn from the study (see Section 7.2).

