Transient, asymptomatic liver function test (LFT) abnormalities, including rare cases of alanine aminotransferase (ALT) and/or aspartate aminotransferase (AST) elevations >10 fold the upper limit of normal (\times ULN), have been reported in several participants in IBSM studies [5,12]. However, changes in bilirubin have only been reported in one participant with undiagnosed pre-existing liver disease [12]. The LFT abnormalities did not require treatment, and resolved by the end of the studies. A few cases of the LFT elevations were considered serious AEs (SAEs) by two Pharma sponsors due to internal processes for SAE notifications. An independent review involving drug-induced liver injury experts found these liver function abnormalities were most likely a direct consequence of the malaria infection rather than a direct drug-induced liver injury caused by the investigational antimalarial drug [13]. As a precaution, participants with LFT results exceeding the acceptable values at screening (Appendix 12.2) will be ineligible to participate in this study. All enrolled participants will undergo regular safety monitoring to assess for asymptomatic liver function abnormalities. Participants will be required to minimise intake of possibly hepatotoxic substances, such as alcohol and paracetamol, during the trial. Drugs of abuse are not permitted under any circumstance.

- **Risk management of cardiac adverse events**

There have been four cardiac SAEs reported in healthy participants in the Netherlands participating in malaria challenge studies using sporozoites (i.e., direct feeds by infected mosquitoes rather than IBSM infection). These four cardiac SAEs are described in the *P. falciparum* 3D7 challenge agent IB; two of the events have also been published as case reports [8, 9]. No cardiac SAEs have been attributed to the challenge agents in IBSM studies. However, in one IBSM trial, two participants (one infected with the *P. falciparum* 3D7 challenge agent and one infected with another malaria challenge agent [*P. falciparum* K13]) developed ventricular extra-systoles that were classified as moderate AEs possibly related to malaria. As a precaution, participants at significant risk of cardiovascular disease are excluded from participating in IBSM studies, and regular safety monitoring, including physical examination and ECG assessments, will be performed.

Risks associated with definitive antimalarial medications

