9.4 STATISTICAL ANALYSES

9.4.1 GENERAL APPROACH

Continuous variables will be summarised with the number of observations (non-missing values), mean, standard deviation (SD), median, quartiles, minimum and maximum. The minimum and maximum values will be presented to the same number of decimal places as recorded in the raw data. The mean, median and SD will be presented to one more decimal place than the raw data. Categorical variables will be summarised with the number of observations and the numbers and percent from each category. Percentages will be rounded to one decimal place, with the denominator being the number of participants in the relevant population with non-missing data. No missing data will be imputed. If required, confidence intervals (CIs) will be two sided and will use 95% confidence levels. Any analyses requiring significance testing will use a two-sided test at the 5% significance level.

The inoculation baseline will be defined as the last available assessment prior to administration of the malaria challenge agent. The IMP baseline will be defined as the last available assessment prior to the administration of the IMP. Unscheduled visits will be excluded from summary tables. Assessments conducted at Early Termination will be excluded from summary tables.

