### Outpatient follow-up period

Study Day	12	13	15	17 d	20 d	22	24 d	27 EOS e
Hours (days) post-IMP dose	96±4 (4)	120±12 (5)	168±24 (7)	216±24 (9)	288±24 (12)	336±24 (14)	384±24 (16)	456±24 (19)
Viral screen blood sample								X
RBC alloantibody blood sample								X
Serum pregnancy test blood sample (WOCBP)								X
Urinalysis sample								X
Adverse events	X	X	X	X	X	X	X	X
Concomitant medications	X	X	X	X	X	X	X	X
Safety serum retention blood sample								X
Full physical exam								X
Symptom directed physical exam	X	X	X	X	X	X	X	
Vital signs	X	X	X	X	X	X	X	X
Malaria clinical score	X	X	X	X	X	X	X	X
Electrocardiograph								X
Haematology blood sample			X			X		X
Biochemistry blood sample			X			X		X
Diary card	X	X	X	X	X	X	X	X
Malaria PCR blood sample	X	X	X	X	X	X	X	X
IMP PK blood sample	X	X	X	X	X			
Definitive antimalarial treatment								X b
Parasite drug resistance blood sample				X a				
Parasite ex vivo growth blood sample	X				X c			
Future malaria research blood sample (if participant consented)	X		X					X

EOS: End of study; IMP: Investigational medicinal product; PK: Pharmacokinetics; PCR: Polymerase chain reaction; RBC: Red blood cell; WOCBP: Women of childbearing potential.

aOne blood sample will be collected for parasite drug resistance assessment only in the event of parasite regrowth. This sample will be collected just prior to initiation of definitive antimalarial treatment.

bDefinitive antimalarial treatment to be initiated on Day 24, or earlier in accordance with the criteria specified in section 4.1 of the protocol.

cOne blood sample will be collected for parasite ex vivo growth only in the event of parasite regrowth. This sample will be collected just prior to initiation of definitive antimalarial treatment.

dVisit not required if participant has previously been administered definitive antimalarial treatment and returned at least one negative malaria PCR result.

eParticipants who withdraw, or are withdrawn or discontinued from the trial, will be asked to attend an early termination visit with assessments equivalent to the Day 27 EOS visit.

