#### 4. STATISTICAL CONSIDERATIONS

Data analysis will be performed according to the Sponsor's representative Standard Operating Procedures (SOPs).

The general analytical approach for all endpoints will be descriptive in nature. All summaries will present the data by dose group as well as by all participants combined.

Unless otherwise stated, the following statistical approaches will be taken:

Continuous variables:	Descriptive statistics will include the number of non-missing values, mean, standard deviation (SD), CV%, median, interquartile range, minimum, and maximum. The minimum and maximum values will be presented to the same number of decimal places as recorded in the raw data; mean and median will be presented to 1 decimal place more than raw data; and SD will be presented to two more decimal places than the raw data. The number of decimals for lab parameters may be reduced if the full presentation of the data includes more than 4 significant figures.
Categorical variables:	Descriptive statistics will include frequency counts and percentages per category. Percentages will be rounded to one decimal place, with the denominator being the number of patients in the relevant population.
Imputation:	No imputation will be performed for missing data.
Confidence intervals (CIs):	CIs will be two-sided and will use 95% confidence levels.
Unscheduled Visits	Unscheduled visits that do not have laboratory data on the same visit date will be excluded from summary tables.
Early termination visit	Assessments conducted at Early Termination will be excluded from visit-based summary tables unless otherwise indicated.

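### Inoculated participants who are not dosed have fewer scheduled safety laboratory sets, and the early-termination rule and IMP-anchored baseline keep their later results out of the by-visit and change-from-baseline tables

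*Protocol*

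**What the plan says.** **Who is not dosed.** Protocol 7.1 gives four criteria, as guidance. They include "A participant experiences an SAE or severe AE" (CTCAE Grade 3 or above) and "A participant returns a positive alcohol or urine drug screen". The other two are a positive SARS-CoV-2 test and any other safety signal that the investigator judges a risk.

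**What happens next.** The participant starts definitive treatment and is phoned daily, with adverse events asked about. Malaria PCR is repeated until one result or more is negative, and then: "The participant will then be withdrawn from the study (see Section 7.2". Section 7.2 lists not being dosed among the reasons for which the investigator may withdraw someone. It asks withdrawn participants to attend an early-termination visit with end-of-study procedures, and has ongoing adverse events followed under 8.3.5.

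**Dosed participants treated early.** Footnote d of the schedule (Protocol 1.3, SAP 3.3) reads "Visit not required if participant has previously been administered definitive antimalarial treatment and returned at least one negative malaria PCR result". It is attached to Days 17, 20 and 24 only, and Protocol 12.1.6 agrees. Outpatient haematology and biochemistry fall on Days 15, 22 and 27.

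**Monitoring.** Protocol 2.2.1: "All enrolled participants will undergo regular safety monitoring to assess for asymptomatic liver function abnormalities".

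**Tables.** Protocol 9.4.1: "Assessments conducted at Early Termination will be excluded from summary tables". SAP 4: "Assessments conducted at Early Termination will be excluded from visit-based summary tables unless otherwise indicated". Protocol 9.4.4 promises by-visit safety summaries against both baselines. SAP 4.2.2 defines an inoculation and a treatment baseline, but SAP 11.3.3, 11.3.4 and 11.3.7 summarise change from treatment baseline alone, and 11.3.3 counts only treatment-emergent abnormalities.

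**The concern.** One secondary objective is the safety of blood-stage malaria infection itself, and the FAS is everyone inoculated. Two of the four no-dose criteria are safety events, so for some participants the end of scheduled follow-up depends on the outcome being described. The liver changes of main interest are, by the protocol's own account, usually without symptoms. They are found by a blood test or not at all.

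The table rules then add to the shorter schedule. The one laboratory set that replaces the missed visits is barred from some or all summary tables, and the change and abnormality tables are anchored on an event, IMP administration, that never took place. At stake is whether the FAS laboratory tables describe all inoculated participants or, after Day 8, only those who were dosed.

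**Working it through.** The documents give no figure to reproduce here. The sample size in Protocol 9.2 is not formally calculated and has no non-dosing input. The check compares the rules and then counts visits.

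**1. Is withdrawal automatic?** Protocol 7.1 says that the participant will be withdrawn; 7.2 says that the investigator may do so. Section 8.2.7.11 shows the same split for one event: a positive COVID-19 test before dosing leads to withdrawal with an early-termination visit where possible, whereas a positive test after dosing leads to resumed study visits. No reason is given for the difference.

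**2. Laboratory sets forgone.** The 24 h and 72 h sets belong to the post-IMP confinement schedule and are not counted. The outpatient sets are Days 15, 22 and 27. The withdrawal day is not fixed. As a guide, the six-dose Riamet course (0 and 8 h, then twice daily) takes about 60 h, so a course begun on Day 8 ends near Day 8 + 60/24 = 10.5. The withdrawal days below are assumptions, and a participant still in the study on Day 15 is assumed to have that day's set.

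| Assumed withdrawal day | Days short of Day 27 | Share of 27 days | Sets forgone | Net of one early-termination set |
|---|---|---|---|---|
| 11 | 27 − 11 = 16 | 59% | 15, 22, 27 (three) | 3 − 1 = 2 |
| 13 | 27 − 13 = 14 | 52% | 15, 22, 27 (three) | 3 − 1 = 2 |
| 15 | 27 − 15 = 12 | 44% | 22, 27 (two) | 2 − 1 = 1 |
| 18 | 27 − 18 = 9 | 33% | 22, 27 (two) | 2 − 1 = 1 |

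**3. Where an undosed participant's data appear.**

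- *Retained:* the FAS tables of inoculum-emergent adverse events, malaria-related events by maximum severity, SAEs, AESIs and events leading to discontinuation (SAP 11.3.1.2.2), and peak malaria score with time to peak (11.3.8, Table B). None is visit-based. Individual results are listed on the FAS.
- *By-visit laboratory, vital-sign and ECG tables:* early-termination values are out under both documents.
- *Abnormality counts:* out under the protocol's unqualified rule. Under the SAP it depends on whether the count is held to be visit-based, which is not stated.
- *Change from baseline:* treatment baseline is the last scheduled observation before the first IMP administration (SAP 4.2.2), so it has no defined value without IMP. Treatment-emergent likewise has no start point; SAP 11.3.1 starts that window at IMP administration.
- *Columns:* dose group is assigned immediately before dosing on Day 8 (Protocol 6.3). SAP 4 tabulates by dose group and all combined, so an undosed participant may appear only in the combined column. The disposition table (SAP 7.1) has no line for inoculated or for inoculated but not dosed.

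**4. How many participants?** No rate is given. With 18 inoculated and an assumed non-dosing probability p, P(at least one) = 1 − (1 − p)^18 and the expected number is 18p.

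| p | P(at least one) | Expected number |
|---|---|---|
| 0.01 | 0.17 | 0.2 |
| 0.05 | 0.60 | 0.9 |
| 0.10 | 0.85 | 1.8 |
| 0.20 | 0.98 | 3.6 |

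One or two such participants would be 1/18 = 5.6% or 2/18 = 11.1% of the FAS.

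**The case against.** The strongest reply is that the main malaria-safety analyses do not depend on visits. The event that prevented dosing is counted in the FAS adverse event tables at its maximum severity. The early-termination visit is a detection step in its own right: it includes haematology, biochemistry, ECG, alloantibodies and viral screen. A value past an AESI threshold at that visit would enter the FAS AESI tables, and a clinically significant one would be followed under 8.3.5. The QTcF category table (SAP 11.3.7) already uses non-scheduled data. Dosed participants received an investigational drug and undosed ones did not, so different follow-up can be defended. All of this stands, and it limits the point.

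It does not answer three things. Adverse event tables count only what is detected, and the documents set no search for new laboratory abnormalities after the early-termination visit. The protocol and SAP disagree on how far that visit's data are excluded. The SAP has also dropped the inoculation-baseline summaries that the protocol promised, and these are the ones that suit undosed participants.

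A reader might go further in three ways that the documents do not support:

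- *That the undosed are the participants with the worst malaria reactions.* Two of the four criteria, the alcohol or drug screen and SARS-CoV-2, are not malaria reactions, and the SAE or Grade 3 criterion is not limited to malaria-related events.
- *That their later data are not collected, or that the promise of regular monitoring is broken.* A full end-of-study set is requested, and the promise in 2.2.1 names no frequency.
- *That they form a within-trial reference for separating malaria effects from drug effects.* No such comparison is planned, and a few participants partly selected on safety could not support one.

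**Conclusion.** The point holds in a limited form. Undosed inoculated participants, including but not only those with a serious, severe or other safety signal before Day 8, have a shorter scheduled laboratory follow-up than dosed participants treated early. The net loss is one or two sets each, for withdrawal assumed between Day 11 and Day 18. Their early-termination results reach no by-visit table and may be left out of the abnormality counts, and their change from baseline is undefined under the SAP. A new asymptomatic abnormality arising after that visit could be missed.

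The malaria-safety objective is not lost, because the FAS adverse event, SAE and AESI tables and the peak score keep these participants. The number affected is probably small and rests on an assumed rate. The case for acting is that a stated exclusion rule can drop safety data related to the outcome, and that preventing this costs very little.

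**What to change.** 1. **Early-termination data.** Reconcile Protocol 9.4.1 with SAP 4. State that early-termination and unscheduled values count in FAS worst-value and abnormality tables, even if they stay out of by-visit rows.
2. **Baseline.** In SAP 11.3.3, 11.3.4 and 11.3.7 and Table B, add change from the inoculation baseline and, for laboratory data, counts of inoculum-emergent abnormalities, on the FAS. This restores what Protocol 9.4.4 promises.
3. **Display.** Add an inoculated-but-not-dosed column beside the dose groups, and matching lines in the disposition table.
4. **Follow-up rule.** Reconcile Protocol 7.1, 7.2, schedule footnote d and 12.1.6 on whether not being dosed means withdrawal from the study. Either keep the existing safety visits for undosed participants who still consent, or state why their follow-up differs. Its length is for the sponsor and investigator to decide.

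Items 1 to 3 cost minor SAP wording and programming, plus one protocol sentence. Item 4 costs protocol wording and, if visits are kept, up to three visits of an existing type for a few participants. No new procedure is needed.
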